7.2.2.2. Summaries of Laboratory Abnormalities

The following summaries (number and percentage of subjects) for treatment-emergent laboratory abnormalities will be provided by lab test and treatment group; subjects will be categorized according to the most severe postbaseline abnormality grade for a given lab test:

- Treatment-emergent laboratory abnormalities
- Treatment-emergent Grade 3 and 4 laboratory abnormalities
- Treatment-emergent Grade 2, 3, and 4 laboratory abnormalities

For all summaries of laboratory abnormalities, the denominator is the number of subjects with any nonmissing postbaseline values up to 30 days after the last dose date of B/F/TAF.

A by-subject listing of all treatment-emergent laboratory abnormalities and treatment-emergent Grade 3 or 4 laboratory abnormalities will be provided by subject ID number and visit in chronological order.

7.2.3. Metabolic Laboratory Evaluations

For metabolite assessments, including fasting glucose and the lipid panel (ie, total cholesterol, triglycerides, LDL, HDL, total cholesterol to HDL ratio), only those measurements under fasting status will be summarized by treatment group and visit using descriptive statistics.

7.2.4. Liver-Related Laboratory Evaluations

Liver-related abnormalities after initial study drug dosing will be examined and summarized using the number and percentage of subjects who were reported to have the following laboratory test values for postbaseline measurements collected in the all B/F/TAF phase of this study:

- Aspartate aminotransferase (AST): (a) $> 3 \times \text{ULN}$, (b) $> 5 \times \text{ULN}$, (c) $> 10 \times \text{ULN}$, (d) $> 20 \times \text{ULN}$
- Alanine aminotransferase (ALT): (a) $> 3 \times \text{ULN}$, (b) $> 5 \times \text{ULN}$, (c) $> 10 \times \text{ULN}$, (d) $> 20 \times \text{ULN}$
- AST or ALT: (a) $> 3 \times \text{ULN}$, (b) $> 5 \times \text{ULN}$, (c) $> 10 \times \text{ULN}$, (d) $> 20 \times \text{ULN}$
- Total bilirubin: (a) $> 1 \times \text{ULN}$, (b) $> 2 \times \text{ULN}$
- Alkaline phosphatase (ALP) $> 1.5 \times \text{ULN}$
- AST or ALT $> 3 \times \text{ULN}$ and total bilirubin: (a) $> 1.5 \times \text{ULN}$, (b) $> 2 \times \text{ULN}$
- AST or ALT $> 3 \times \text{ULN}$ and total bilirubin $> 2 \times \text{ULN}$ and ALP $< 2 \times \text{ULN}$

The summary will include data from all postbaseline visits up to 30 days after the last dose date of B/F/TAF. For individual laboratory tests, subjects will be counted once based on the most severe postbaseline value. For both the composite endpoint of AST or ALT and total bilirubin, and the composite endpoint of AST or ALT, total bilirubin, and ALP, subjects will be counted once when the criteria are met at the same postbaseline visit date. The denominator is the number of subjects in the All B/F/TAF Analysis Set with nonmissing postbaseline value of the tests in evaluation at the same postbaseline visit date.

Subjects with AST or ALT $> 3 \times \text{ULN}$ will also be listed.

In addition, baseline, postbaseline, and change from baseline in AST, ALT, ALP, and total bilirubin will be summarized by treatment group and visit using descriptive statistics.

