#### **7.5.5.1. Management of ALT Flare in Subjects Receiving Study Medication**

If laboratory results indicate elevation of ALT  $> 2 \times$  Day 1 value and  $> 10 \times$  ULN, the following is recommended:

- Schedule the subject to return to the clinic as soon as possible (ideally within 3 days after initial laboratory results were drawn). During the visit, a clinical assessment of the subject will be performed. The assessment should include a physical examination and evaluation of the subject's mental status.
- If the ALT elevation is confirmed, request the central clinical laboratory to conduct reflex testing for plasma HBV DNA, HBV serology (HBsAg and HBsAb), HDV, HAV IgM, and HCV serology

Check the following laboratory parameters: serum ALT and AST, total bilirubin, INR, and serum albumin. Based on the results of the confirmatory tests, the following treatment modifications are recommended:

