7.2. Laboratory Evaluations

Laboratory data will be analyzed and summarized using both quantitative and qualitative methods using All B/F/TAF Analysis Set. The analysis will be based on values reported in conventional units. When values are below the LOQ, they will be listed as such, and the imputed value will be used for the purpose of calculating summary statistics as specified in Section 3.7.

A by-subject listing for laboratory test results will be provided by subject ID number and visit in chronological order for hematology, serum chemistry, and urinalysis separately for all data collected from both phases of the study. Values falling outside of the reference range and/or having a severity grade of 1 or higher on the Gilead Grading Scale for Severity of Adverse Events and Laboratory Abnormalities will be flagged in the data listings, as appropriate.

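### The liver composites in SAP 7.2.4 count only same-date elevations, so a bilirubin rise first seen after AST and ALT are back at or below 3 x ULN is listed but not tabulated

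*SAP*

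**What the plan says.** SAP section 7.2.4 (Liver-Related Laboratory Evaluations) has single-test rows and composite rows. The composites are AST or ALT > 3 x ULN with total bilirubin > 1.5 x ULN or > 2 x ULN, and AST or ALT > 3 x ULN with bilirubin > 2 x ULN and ALP < 2 x ULN.

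- **Single tests:** "subjects will be counted once based on the most severe postbaseline value", whatever its date.
- **Composites:** "For both the composite endpoint of AST or ALT and total bilirubin, and the composite endpoint of AST or ALT, total bilirubin, and ALP", the rule is that "subjects will be counted once when the criteria are met at the same postbaseline visit date".
- **Denominator:** women in the All B/F/TAF Analysis Set with a "nonmissing postbaseline value of the tests in evaluation at the same postbaseline visit date".
- **Data used:** "The summary will include data from all postbaseline visits up to 30 days after the last dose date of B/F/TAF". Unscheduled draws are therefore eligible.
- **Listings:** subjects with AST or ALT > 3 x ULN "will also be listed". SAP section 7.2 adds, for serum chemistry among others: "A by-subject listing for laboratory test results will be provided by subject ID number and visit in chronological order".

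Neither section states a time window between the enzyme and bilirubin elevations or a count of non-concurrent elevations, and I found none elsewhere in the SAP.

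**The concern.** Bilirubin can rise later than the transaminases. If AST and ALT are both at or below 3 x ULN on the date bilirubin first passes 2 x ULN, no single date meets the rule. The woman then contributes to the AST/ALT > 3 x ULN row and to the bilirubin > 2 x ULN row, and no table shows that the two entries are one person.

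The topic matters in this trial. Protocol sections 1.11 and 7.5.4 describe hepatobiliary findings in monkeys at the high dose, and 7.5.4 calls the risk to humans at the clinical dose unknown. The composite counts are likely to be small, so one woman more or less would be visible in the table.

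**Working it through.** The plan states no figure that depends on this rule, so there is nothing to reproduce. The check applies the rule to constructed cases and then to the visit schedule.

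**Rules compared.** Let A be the higher of AST and ALT, and B total bilirubin, both in multiples of ULN.

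- Same date (SAP 7.2.4): some date has A > 3 and B > 2.
- Forward window W: A > 3 on date d1 and B > 2 on date d2, with 0 ≤ d2 − d1 ≤ W.
- Any time: the maximum of A exceeds 3 and the maximum of B exceeds 2.

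**Constructed cases.** All values are hypothetical, and bilirubin is 1.0 x ULN on the first date. The 14- and 30-day windows are assumptions.

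| Case | First date | Second date | Same date | 14 days | 30 days | Any time |
|---|---|---|---|---|---|---|
| A | day 84: A = 8 | day 91: A = 4, B = 2.5 | yes | yes | yes | yes |
| B | day 84: A = 8 | day 98: A = 2.5, B = 2.5 | no | yes | yes | yes |
| C | day 56: A = 4 | day 84: A = 2, B = 2.5 | no | no | yes | yes |
| D | day 84: A = 4 | day 168: A = 1.5, B = 2.5 | no | no | no | yes |

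Case A shows that a rise after the peak still counts while an enzyme is above 3 x ULN. Cases B to D show the gap. The bilirubin > 1.5 x ULN composite does not rescue them: bilirubin is 1.0 when A > 3, and A ≤ 3 when bilirubin is 2.5.

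**How long A stays above 3 x ULN.** With exponential decline from peak P and half-life h, the time is t = h × log2(P/3). The half-lives are assumed; the documents give none.

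| Peak P (x ULN) | h = 2 days | h = 7 days | h = 14 days |
|---|---|---|---|
| 5 | 1.5 | 5.2 | 10.3 |
| 10 | 3.5 | 12.2 | 24.3 |
| 20 | 5.5 | 19.2 | 38.3 |

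Example: 7 × log2(10/3) = 7 × 1.737 = 12.2 days.

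**Against the schedule.** Randomized-phase visits fall at Weeks 4, 8, 12, 24, 36 and 48 (SAP 1.2). The gaps are 4 × 7 = 28 days to Week 12 and 12 × 7 = 84 days afterwards. Extension visits are also 84 days apart (protocol 6.5.1). Only one value in the table (38.3 days) exceeds 28 days, and none reaches 84. If draws occur only at scheduled visits, the same-date rule will usually miss a lagged pair.

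**Against repeat testing.** Protocol 7.5 asks for repeats within 3 calendar days of receiving results for clinically significant Grade 3 and 4 abnormalities. Appendix 4 grades AST/ALT > 2.50 to 5.00 x ULN as Grade 2, so a value between 3 and 5 x ULN has no repeat required by that rule. The flare procedure in 7.5.5.1 does require linked draws ("Check the following laboratory parameters: serum ALT and AST, total bilirubin, INR, and serum albumin"), followed by weekly monitoring, but only for ALT > 2 x Day 1 and > 10 x ULN. From a peak of 10 x ULN, ALT stays above 3 x ULN through 0 weekly draws at h = 2 (3.5/7 = 0.5), 1 at h = 7 (12.2/7 = 1.7) and 3 at h = 14 (24.3/7 = 3.5). Close follow-up therefore makes a same-date pair more likely to be seen, but does not guarantee it.

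**The case against.** The strongest reply is that no case is hidden. Every woman at issue has AST or ALT > 3 x ULN and so is listed by name of the criterion alone, whatever her bilirubin. Her chemistry results are also listed in date order, with abnormal values flagged. Hepatic adverse events are summarised separately from 15 SMQs (SAP 7.1.7.3 and Appendix 4), and protocol 7.5.4 requires prompt contact with the medical monitor about laboratory signs of hepatobiliary toxicity. The analysis is descriptive. This stands, and it keeps the point small.

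It does not remove the point. A listing does not put the woman in the reported count. SAP 7.2.4 does not say that the AST/ALT listing shows bilirubin or ALP. Adverse-event coding is not a full backstop, because protocol 7.1.3 does not record laboratory abnormalities without clinical significance as adverse events.

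A reader might infer more than the documents support:

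- **That any bilirubin rise after the transaminase peak is missed.** The test is > 3 x ULN on the bilirubin date, not at the peak (case A).
- **That the composite is the SAP's definition of, or main screen for, drug-induced liver injury.** The SAP uses neither label; these are rows in a laboratory summary.
- **That one missed woman turns a conclusion of none into some.** No stated conclusion rests on this cell. The rule of three gives upper 95% bounds of 3/235 = 1.3% and 3/470 = 0.6% after zero events, taking the planned sizes as the range of women exposed. That describes the precision of a zero count, not how often the rule misses a case.
- **That the flare procedure creates the gap.** It starts above 10 x ULN, so a peak of 8 x ULN, as in case B, does not trigger it.

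**Conclusion.** The point holds as a minor one. The composite rows in SAP 7.2.4 omit a woman whose bilirubin is first seen above 2 x ULN when both AST and ALT are already at or below 3 x ULN. She remains in the listings. The size is a possible undercount in one descriptive B/F/TAF-only table of the final analysis. Its frequency cannot be estimated from the documents. The gap follows from the wording alone. The statement that scheduled visits will usually miss a lagged pair rests on the assumed half-lives of 2 to 14 days and peaks of 5 to 20 x ULN. The primary endpoint and its non-inferiority conclusion are untouched. The SAP for the Week 48 comparison is not among the documents, so nothing is said here about its liver tables.

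**What to change.** 1. Keep the same-date rows unchanged.
2. Add a supplementary count of women with total bilirubin > 2 x ULN on the same date as, or within a prespecified window after, AST or ALT > 3 x ULN. Thirty days is one possible choice; the documents give no window.
3. Report it with and without ALP < 2 x ULN, taking ALP on the date of the qualifying AST/ALT value.
4. Use as denominator the women with at least one nonmissing postbaseline value of each test in the row, since the same-date denominator does not fit a non-concurrent pair.
5. State that the AST/ALT > 3 x ULN listing shows serial bilirubin and ALP.

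The cost is a few sentences of SAP text, two table rows and extra listing columns, all from data already collected. The downside is a few extra, possibly unrelated, cases to review. The gain is also limited: with visits 84 days apart after Week 12, a 30-day window will then mainly add unscheduled, early-discontinuation and follow-up draws, and a pair such as case D stays uncounted. If the change is made after the SAP is final, SAP section 1 requires it to be documented in the clinical study report.

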7.2.5. Renal-Related Laboratory Evaluations

7.2.5.1. Serum Creatinine and eGFR_{CG}

Baseline, postbaseline, and change from baseline in serum creatinine and eGFR_{CG} will be summarized by treatment group and visit using descriptive statistics.

7.2.5.2. Urine Creatinine, Urine Retinol Binding Protein to Creatinine Ratio, and Beta-2-Microglobulin to Creatinine Ratio

Baseline, postbaseline, and change from baseline in urine creatinine will be summarized by treatment group and visit using descriptive statistics.

Baseline, postbaseline, change from baseline, and percentage change from baseline in urine RBP to creatinine ratio and beta-2 microglobulin to creatinine ratio will be summarized by treatment group and visit using descriptive statistics.

7.2.5.3. Albuminuria by Quantitative Assessment

The baseline, postbaseline, changes from baseline, and percentage change from baseline in UACR will be summarized by treatment group and visit using descriptive statistics.

The number and percentage of subjects with UACR < 30 mg/g versus \geq 30 mg/g will be summarized by baseline category at Weeks 24, 48, 72, 96, and based on the last on-treatment value (ie, data collected after the first dose date up to 1 day after the last dose date of B/F/TAF) {KDIGO Guideline Development Staff 2013}.

7.3. Body Weight, Height, and Vital Signs

Descriptive statistics will be provided by treatment group for vital signs and body weight as follows:

- Baseline values
- Values at each postbaseline analysis window
- Change from baseline at each postbaseline analysis window

A baseline value will be defined as the last nonmissing value obtained on or prior to the date of first dose of B/F/TAF. Change from baseline to a postbaseline visit will be defined as the postbaseline value minus the baseline value.

In the case of multiple values in an analysis window, data will be selected for analysis as described in Section 3.8.3. No formal statistical testing is planned.

A by-subject listing of vital signs will be provided by subject ID number and visit in chronological order. In the same listing, a by-subject listing of body weight, height, and BMI will be provided.

7.4. Prior and Concomitant Medications

7.4.1. Antiretroviral Medications

Any nonstudy ARV medications used prior to, during, or after the study (if collected) are all recorded on the ARV eCRF. All ARV medications recorded on the ARV eCRF will be coded using the Gilead-modified World Health Organization (WHO) Drug Dictionary for ARV medication. The WHO preferred name and drug code will be attached to the clinical database. All ARV medications recorded on the ARV eCRF will be listed. No inferential statistics will be provided.

7.4.2. Concomitant Non-Antiretroviral Medications

Concomitant non-ARV medications are defined as non-ARV medications taken while a subject took study drug. Use of concomitant non-ARV medications from the first dose date to the last dose date of B/F/TAF will be summarized by preferred name using the number and percentage of subjects for each treatment group. Multiple drug use (by preferred name) will be counted only once per subject. The summary will be sorted by decreasing order of total frequency.

If the start or stop date of non-ARV medications is incomplete, the month and year (or year alone, if month is not recorded) of the start or stop date will be used to determine whether the non-ARVs are concomitant or. The medication is concomitant if the month and year of the start or stop (or year of the start or stop, if month is not recorded) of the medication does not meet either of the following criteria:

- The month and year of start of the medication is after the last dose date of B/F/TAF
- The month and year of stop of the medication is before the first dose date of B/F/TAF

If the start and stop date of non-ARV medications are complete, the start date is not after the last dose date and the stop date is not before the first dose date, or the non-ARV medications are marked as ongoing and start date is on or before the last dose date, the non-ARV medications are concomitant for the all B/F/TAF phase of the study.

Summaries of non-ARV concomitant medications will be provided for the All B/F/TAF Analysis Set. Subjects with any non-ARV concomitant medications will be listed including Anatomical Therapeutic Chemical (ATC) drug class level 2. No inferential statistics will be provided.

7.5. Electrocardiogram Results

A shift table of the investigators' assessment of ECG results at each scheduled postbaseline visit compared with baseline values will be presented by treatment groups using the following categories: normal; abnormal, not clinically significant; abnormal, clinically significant; or missing. The number and percentage of subjects in each cross-classification group of the shift table will be presented. Subjects with a missing value at baseline or postbaseline will not be included in the denominator for percentage calculation. No inferential statistics will be provided.

A by-subject listing for ECG assessment results will be provided by subject ID number and visits in chronological order.

7.6. Other Safety Measures

A data listing will be provided for subjects experiencing pregnancy during the study. Physical examination was not collected in the eCRF. Therefore, it will not be included in the analysis.

7.7. Subgroup Analyses for Safety Endpoints

Subgroup analysis by prior treatment regimen (ie, TDF-containing regimen versus non-TDF containing regimen) will be performed for renal endpoints including urine RBP to creatinine ratio, beta-2 microglobulin to creatinine ratio, and UACR using All B/F/TAF Analysis Set, as described in Section 7.2.5 above.

7.8. Changes From Protocol-Specified Safety Analyses

No change from protocol-specified safety analysis is planned.

8. PHARMACOKINETIC ANALYSES

All necessary PK analyses have been performed as part of the Week 48 analysis and will not be repeated in this analysis.

10. SOFTWARE

SAS[®] Version 9.4 (SAS Institute Inc., Cary, NC, USA) is to be used for all programming of tables, listings, and figures.

nQuery Advisor[®] Version 6.0 (Statistical Solutions, Cork, Ireland) is to be used for sample size and power calculation.

11. SAP REVISION

Revision Date (dd month, yyyy)	Section	Summary of Revision	Reason for Revision

12. APPENDICES

- Appendix 1. Study Procedures Table
- Appendix 2. TFL Mocks
- Appendix 3. Cardiovascular or Cerebrovascular Events
- Appendix 4. Hepatic Events
- Appendix 5. Programming Specification

Appendix 1. Study Procedures Table

Study Procedure	Screening ^a	Day 1 ^b	End of Week ^c						Post Week 48 ^{d,v} Every 12 Weeks	30 Day Follow-Up ^e	ESDD ^f
			4	8	12	24	36	48			
Informed Consent	X										
Medical History	X										
Concomitant Medications	X	X	X	X	X	X	X	X	X	X	X
Adverse Events	X	X	X	X	X	X	X	X	X	X	X
Complete Physical Exam	X	X				X		X			X
Symptom-Directed Physical Exam			X	X	X		X		X	X	
12-Lead ECG	X	X				X		X			X
Height	X										
Weight	X	X	X	X	X	X	X	X	X	X	X
Vital Signs ^g	X	X	X	X	X	X	X	X	X	X	X
Urinalysis	X	X	X	X	X	X	X	X	X	X	X
Urine Chemistry ^h		X				X		X	X ^w		
Urine Pregnancy Test ⁱ		X	X	X	X	X	X	X	X	X	X
Serum Pregnancy Test ⁱ	X										
Chemistry Profile ^j	X	X	X	X	X	X	X	X	X	X	X
Metabolic Assessments ^k		X			X	X		X	X ^w		
Estimated GFR	X	X	X	X	X	X	X	X	X	X	X
Hematology Profile ^l	X	X	X	X	X	X	X	X	X	X	X
Plasma HIV-1 RNA ^m	X	X	X	X	X	X	X	X	X	X	X
CD4+ Cell Count	X	X	X	X	X	X	X	X	X	X	X
HBV Blood Panel ⁿ	X										

Study Procedure	Screening ^a	Day 1 ^b	End of Week ^c						Post Week 48 ^{d,v}	30 Day Follow-Up ^e	ESDD ^f
			4	8	12	24	36	48	Every 12 Weeks		
Plasma HBV DNA ^o		X			X	X		X	X ^w		X
HCVAb ^p	X										
HCV RNA ^p	X					X		X	X ^w		
HIV-1 Genotype/Phenotype ^q								X ^q			X ^q
Single PK Draw ^r				X		X	X				
Trough PK Draw ^s			X		X						
PK Sample (post-dose) ^s			X		X						
Observed In-Clinic Dose ^s			X		X						
Provide Dosing Diary ^u		X	X	X	X	X					
Collect Dosing Diary ^x			X	X	X	X	X				
CCI											
CCI											
Randomization		X									
Study Drug Dispensation		X	X	X	X	X	X	X ^v	X ^v		
Study Drug Accountability			X	X	X	X	X	X	X		X

- a Evaluations to be completed within 30 days prior to Day 1.
- b Subjects should initiate dosing of study drug on the same day as the Day 1 visit.
- c All study visits should be ± 2 days of the protocol-specified visit date based on the Day 1 visit through Week 12 and completed within ± 6 days at Week 24 and Week 36, unless otherwise specified. The visit window at Week 48 will be ± 6 weeks of the protocol-specified visit date.
- d At the Week 48 Visit, subjects in a country where GS-9883/F/TAF FDC is not available will be given the option to receive GS-9883/F/TAF FDC for an additional 48 weeks, or until the product becomes accessible to subjects through an access program, or until Gilead Sciences elects to discontinue the study in that country, whichever occurs first. Study visits are to be completed every 12 weeks, within ± 6 days of the protocol-specified visit date unless otherwise specified.

- e Must be completed 30 days after discontinuing study drug. For the purpose of scheduling a 30-Day Follow-Up Visit, a ± 6 days window may be used. Required for subjects who permanently discontinue study drug prior to Week 48 and do not continue in the study through at least one subsequent visit after the ESDD visit. Subjects who participate post Week 48 will be required to return to the clinic 30 days after the completion of study drugs for the 30-Day Follow-Up Visit.
- f Early Study Drug Discontinuation visit to occur within 72 hours of last dose of study drug. Subjects will be asked to continue attending the scheduled study visits through the Week 48 Visit even if the subject discontinues study drug.
- g Vital signs measurements including blood pressure, pulse, respiratory rate, and temperature
- h Urine Chemistry includes urine albumin, urine creatinine, urine protein, retinol binding protein, and beta-2 microglobulin
- i Women of childbearing potential only. Positive urine pregnancy tests will be confirmed with a serum test.
- j Chemistry profile: alkaline phosphatase, AST, ALT, GGT, total bilirubin, direct and indirect bilirubin, total protein, albumin, bicarbonate, BUN, calcium, chloride, creatinine, glucose, phosphorus, magnesium, potassium, sodium, uric acid, and amylase (reflex lipase testing is performed in subjects with total amylase $> 1.5 \times$ ULN). At Day 1, Weeks 24, and 48 and every 24 weeks during the post Week 48 period, analyses of glucose will be done as part of the fasting metabolic assessments and not as part of the chemistry profile. TSH will be collected at Screening, Day 1, Weeks 24, and 48, as well as every 24 weeks post Week 48, and ESDD if applicable.
- k Fasting glucose and lipid panel (total cholesterol, HDL, direct LDL, triglycerides). If the subject has not fasted prior to the visit, the visit may proceed, but the subject must return within 72 hours in a fasted state to draw blood for the metabolic assessments.
- l CBC with differential and platelet count.
- m If the HIV-1 RNA value is ≥ 50 copies/mL at Week 48, a retest HIV-1 RNA value must be collected within two to three weeks of the initial test.
- n Hepatitis B Virus (HBV) blood panel: Hepatitis B virus surface antigen (HBsAg), Hepatitis B virus surface antibody (HBsAb) and Hepatitis B virus core antibody (HBcAb). If positive HBsAg, reflex testing for plasma HBV DNA, HBeAg (if negative, reflex HBeAb), and quantitative HBsAg. If positive HBcAb with negative HBsAg and negative HBsAb, reflex testing for plasma HBV DNA (if positive, reflex HBeAg). If HBeAg is performed and found to be negative, reflex HBeAb.
- o For subjects who meet the definition of HBV infection, the following will be conducted by the central laboratory: HBsAb, HBsAg (qualitative and quantitative) and HBeAg (if negative, reflex HBeAb) at Days 1, 12, 24 and then every 24 weeks.
- p Subjects who are HCVAb positive will have a HCV RNA test performed at screening and every 24 weeks.
- q HIV-1 genotype/phenotype testing for subjects with HIV-1 RNA ≥ 200 copies/mL and virologic rebound, at early study drug discontinuation or Week 48. Following unconfirmed virologic rebound, subjects will be asked to return to the clinic (2-3 weeks later) prior to the next scheduled visit or at the next scheduled study visit, for a HIV-1 RNA and HIV-1 genotype/phenotype (reverse transcriptase, protease and integrase) blood draw. Based on the results of this testing, subjects should be managed according to the Virologic Rebound Schema (Section 6.13.1).
- r All subjects on GS-9883/F/TAF (Treatment Group 1 only) will have a single anytime PK blood sample collected at Weeks 8, 24 and 36.
- s Subjects on GS-9883/F/TAF (Treatment Group 1 only) will have a Trough PK blood sample collected between 20-28 hours following their last dose at Weeks 4 and 12. Subjects must be instructed to not take their study drugs on the morning of their visit for the trough sample collection. If the subject has taken their dose of study drugs prior to the visit, the visit may proceed, but the subject must return within 72 hours for the single trough PK blood sample collection. In the event a subject routinely takes their study drug in the evening, a single anytime sample may be drawn at Weeks 4 and 12 as the subject will not be instructed to change their dosing time to accommodate this trough PK draw. A post-dose PK blood sample will be collected between 1 and 4 hours post dose following an observed, in-clinic dose.
- t [REDACTED]
- u A dosing diary will be dispensed for all Treatment Group 1 subjects to complete prior to each of the PK sample visits.
- v Open-label GS-9883/F/TAF FDC will be dispensed to subjects participating in the study post Week 48 starting at the Week 48 Visit.
- w Every 24 weeks only.
- x Dosing diaries will be collected from subjects for the single anytime PK and trough PK collection (Treatment Group 1 only). If a dosing diary is not returned the site may ask the subject for the time of the last dose and if it was taken with or without food.

